scientists are appropriately cautious realizing that such technology is far from being practical and affordable for all individuals who would benefit. However, an off-the-shelf AFO is the least complex form of exoskeleton, that is easily adjustable, affordable, and available to immediately be prescribed and worn by patients with PAD wishing to walk further who do not wish or are not candidates to undergo an operation.

Research Plan

Study Design: We plan to recruit 50 patients with PAD from the claudication clinic at the Nebraska and Western Iowa Veterans Affairs' Medical Center (VAMC) in Omaha, Nebraska (Figure 13). As we just completed enrollment of a five-year NIH grant that included 200 patients (R01 AG034995) and have collected over 50 patients in 18 months for a COBRE research project (P20 GM109090), we expect this recruitment goal to be attainable. The collaborating vascular surgeons, Drs. [name] and [name], will evaluate all patients seen at the University of Nebraska Medical Center and Veterans' Affairs Medical Center claudication clinics. The PI also participates in these clinics and works side by side with the surgeons.

Inclusion criteria: At entry into the study, all subjects must:

- 1) be able to give written, informed consent
- 2) demonstrate positive history of chronic claudication
- 3) demonstrate exercise-limiting claudication established by history and direct observation

during a screening walking test administered by the evaluating vascular surgeon.

- 4) have an ankle/brachial index < 0.90 at rest⁶⁹
- 5) and have a stable blood pressure regimen, stable lipid regimen, stable diabetes regimen and risk factor control for 6 weeks.

Exclusion criteria: Any potential subjects will be excluded if they have:

- 1) rest pain or tissue loss due to PAD (Fontaine stage III and IV)⁶⁹
- 2) acute lower extremity ischemic event secondary to thromboembolic disease or acute trauma
- 3) walking capacity limited by conditions other than claudication including leg (joint/musculoskeletal, neurologic) and systemic (heart, lung disease) pathology

Specific Aim 1: Determine the acute impact of the AFO on walking performance

Approach: We propose to study 50 patients with PAD, measuring walking performance with and without wearing a carbon composite AFO. Patients will wear the AFO on the affected leg(s), so patients with bilateral leg symptoms will wear them on both legs while patients with unilateral disease will wear the AFO on the symptomatic leg only. Walking performance will include measurement of initial and absolute walking distances, and lower extremity torque and power. Energy cost and muscle activity will be tested as potential mechanisms contributing to improvement in walking performance. Conditions will be randomized, with half of the subjects performing the tests without the AFO and the other half starting with the AFO walking conditions. All data will be collected in the Biomechanics Research Building (BRB). All subjects will be consented after reporting to the BRB and the outcomes detailed below will be assessed. The entire process is expected to take 2.5 hours.

Outcomes

- 1) **Initial and absolute walking distances:** Walking distances will be determined with a progressive-load treadmill test⁶⁷ with initial and maximum claudication distances as outcomes. During the treadmill test, patients will walk on a treadmill that starts at 0% grade and 2.0 mph. Every two minutes, the grade will be increased by 2% up to a maximum of 15% grade, and the speed held constant throughout the test⁶⁷.
- 2) **Lower extremity torque and power:** Biomechanical data will be collected using eight in-ground AMTI force platforms and a 12 camera high speed digital motion capture system (Cortex 5.1, Motion Analysis Corp, Santa Rosa, CA) to collect three dimensional kinematics (60 Hz) and kinetics (ground reaction forces, 600 Hz). Reflective markers will be placed at specific anatomical locations on the lower limbs, utilizing the marker systems of Vaughan⁷⁰ and Nigg⁷¹. Following the setup, kinematics and ground reaction forces will be recorded while the subjects walk with their self-selected pace through a ten-meter pathway. Each patient will be tested before the onset of claudication pain (pain free) with a mandatory one-minute rest period between the walking trials to insure that all trials are in a pain free condition. A total of five walking trials per leg will be collected. Following the collection of overground data, the patients with PAD will be allowed to rest.

Data are exported and processed in custom laboratory software using MATLAB (Mathworks Inc., MA) and Visual 3D (C-Motion, Inc., MD). This software is used to calculate ground reaction forces for the vertical, anterior-posterior, and medial-lateral direction, and joint angles and joint angular velocity for the hip, knee, and ankle during the stance phase of walking. Lower extremity joint muscular responses and contributions during walking are determined using joint torques and powers. Joint torques and powers are calculated using inverse dynamics for the hip, knee, and ankle during the stance phase of walking. Inverse dynamics combine the kinematics and the ground reaction forces as described by Winter⁷². Additionally, spatial and temporal characteristics will be calculated using custom code in MATLAB (Mathworks Inc., MA). From this data our primary lower extremity function outcome measures will be ankle and hip plantarflexor torque and power, although all kinematic and kinetic measures of the lower extremity will be investigated.

- 3) **Muscle activity:** Electromyographic data will be collected from the gastrocnemius and soleus muscles of the affected legs at 1000 Hz using surface electrodes with the DelSys Trigno™ wireless system. Prior to the trials maximum voluntary contraction electromyographic signals will be recorded for each muscle via isometric contraction for three seconds. For electromyographic data analysis, time-domain and frequency-domain analyses will be performed using custom Matlab programs. Time-domain analysis of electromyographic signal provides a measure of the average muscle activity and work produced by a given muscle (activation profiles)⁷³. The mean electromyographic signal (EMG_{mean}) will be computed to measure the average muscle activity for each trial. The electromyographic envelope (EMG_{env}) will also be calculated by integrating the time series of root-mean-square electromyographic signal for each trial. EMG_{env} provides a measure of the muscle work for a given trial. Frequency-domain analysis of

electromyographic signal provides a window into muscle fatigue and motor unit recruitment⁷³. The raw electromyographic signal will be converted to the frequency domain using a Fast Fourier Transform to determine the power spectrum. Median frequency and frequency bandwidth will be computed from the power spectrum. Median frequency will be computed as the frequency at half of the integrated power spectrum as given by the following equation (1)⁷³:

$$(1) \int_0^{f_{med}} P(f)df = \int_{f_{med}}^{f_{max}} P(f)df \int_0^{f_{med}} P(f)df = \int_{f_{med}}^{f_{max}} P(f)df$$

where $P(f)$ is the power at frequency f , f_{med} is the median frequency, and f_{max} is the maximum frequency of the power spectrum. Frequency bandwidth (f_{band}) is the difference between the highest and lowest frequency where the power exceeds half the maximum power of the power spectrum.

4) **Energy cost:** A portable metabolic cart (Cosmed K4b2, Cosmed USA Inc., Chicago, IL), will be used to measure gas exchange on a breath-by-breath basis, providing a measure of oxygen consumption. Steady-state oxygen consumption in ml/kg/min will be calculated during the walking distance test.

Statistical analysis: The sample size was calculated to detect effect sizes observed in pilot data for initial and absolute walking distances. The mean (SD) difference in initial walking distance with and without AFO was 43.4 meters (93), corresponding to a standardized effect size of 0.47 standard deviations. A sample size of 50 subjects will provide 84% power to detect differences of 0.47 standard deviations between walking with and without an AFO, using a paired t-test for sample size estimation purposes only, and a significance level of 0.02 to informally adjust for multiple testing. The standardized effect size for absolute walking distance was 1.29 standard deviations, so the sample size of 50 subjects will also provide sufficient power to detect this difference. For statistical analysis, a linear (or generalized linear, as appropriate) mixed modeling approach will be used. This approach will allow us to detect differences between walking with and without an AFO while adjusting for confounding variables. The level of significance will be set at 0.05.

Expected results/possible limitations: Based on work with AFO devices in other pathological populations, we expect the AFO will improve lower extremity torque and power generation enough to demonstrate a clinically important difference. If our hypothesis is correct, the AFO will be a potential new conservative intervention for improving walking performance in patients with PAD, along with the mechanisms contributing to those improvements. If our hypothesis is not supported, we speculate that the AFO may still be a viable conservative treatment option based on results of Specific Aim 2. For example, the AFO may improve walking performance over the course of the three-month intervention. This aim will also provide data on muscle contribution that could be used to design and test an improved AFO. Our preliminary work looks promising for increasing the distance that patients with PAD can walk. Completion of this aim will provide the groundwork for exploring and designing even more effective AFO devices.

Specific Aim 2: Determine improvements in walking performance following a three month AFO intervention

Approach: We propose to study a subset of 30 patients from Specific Aim 1 measuring walking performance, physical activity, and quality of life after a three-month AFO intervention. Walking performance will be assessed in the same manner as in Specific Aim 1 during the baseline assessment. Physical activity will be assessed using accelerometers while quality of life will be assessed through questionnaires. To investigate mechanisms contributing to improvements in walking performance, physical activity and quality of life, we will measure changes in energy cost, muscle morphometric parameters, muscle oxygenation, and muscle strength and endurance at baseline and following each of the three month intervention arms (control and AFO).

AFO and Control Intervention: Patients will be asked to wear an AFO each day for three months. Subjects will have an off-the-shelf AFO (Figure 2) chosen initially based on shoe size and adjusted or exchanged for a different size during the initial evaluation after entering the study. The patients will be asked to wear the AFO at all times except when they are in bed or showering/bathing. The instructions given to the patients about walking will be the same as typically provided by clinicians, which is to walk 30 minutes per day, most days/week. We have chosen this specific AFO device because it is already available for use in a clinical environment, is composed of a carbon-composite material that will capture and return energy during the gait cycle, and has successfully contributed to propulsion during walking in other clinical populations^{26, 28}. Patients will be able to contact the nurse coordinator at any time if they need the AFO adjusted or have questions about what should happen during the intervention. Subjects in the control arm will be asked to continue the same lifestyle for three months. The intervention arm order will be randomized (see Statistical Analysis)

Outcomes: All outcomes will be assessed at baseline and following each arm (control and AFO).

- 1) Initial and absolute walking distances, 2) Lower extremity torque and power, 3) Muscle activity, and 4) Energy cost will all be measured as described for Specific Aim 1.
- 5) **Physical Activity:** Participants will wear the Actigraph (Actigraph GT3X, Actigraph, FL, USA) accelerometer on their hip for seven days (the whole day except when sleeping) prior to starting the AFO intervention to measure baseline activity level. The accelerometer will be mailed back to researchers in a pre-paid envelope. Two weeks prior to the post-intervention visit to the laboratory, an accelerometer will be mailed to participants to wear the final seven days before the visit. Average steps/day, maximum cadence, and average peak activity index will be calculated.
- 6) **Quality of Life:** The Walking Impairment Questionnaire⁷⁴, Medical Outcomes Short Form 36, and Edinburgh Claudication Questionnaire will be used to assess quality of life. The Walking Impairment Questionnaire has been validated in patients with claudication⁷⁴ and the Short Form 36 has been extensively evaluated and tested with a variety of populations and is able to distinguish between groups of varying health status^{75, 76}. The Edinburgh Claudication Questionnaire was developed in an iterative, systematic fashion and has been implemented as a more holistic approach to identify presence of intermittent claudication in many clinical trials.^{20, 77-82}
- 7) **Morphometric parameters:** An ultrasound transducer (LS128 CEXT-1Z, Telemed, LT, Lithuania) will be used to assess thickness of the plantarflexor muscles using a standard real time B-mode image. Muscle thickness will be measured on the posterior medial and lateral surfaces, 20, 30, and 40% between the lateral malleolus of fibula and the lateral condyle of the tibia. The average values of muscle thickness at all measured sites will be the primary outcome measure.
- 8) **Muscle Oxygenation:** Continuous-wave near infrared spectroscopy (Moxy Monitor, Fortiori Design LLC, MN, USA) will be measured bilaterally on the gastrocnemius calf muscle before, during and after the walking distance test. We will measure resting StO₂, minimum StO₂ during the maximal treadmill test, time to minimum StO₂, and the StO₂ recovery time.
- 9) **Muscle Strength and Endurance:** An isokinetic dynamometer (Biodex 4 Medical Systems, Inc. USA) will be used to measure peak isokinetic strength (torque) of the ankle and hip of the more symptomatic leg. Peak torque and total work performed for ankle plantarflexion, ankle dorsiflexion, hip flexion, and hip extension will be measured. Subjects will perform one trial of five repetitions at 60 degrees/second to assess strength, and one trial of 15 repetitions at 120 degrees/second to assess endurance.

Statistical analysis: A portion of patients from Aim 1 will be randomized to one of two intervention arms (control then AFO, or AFO then control). We expect differences from a 3-month training to be larger than the immediate differences shown in Aim 1. A sample size of 30 subjects (15 per treatment arm) will provide 80% power to detect differences of 0.59 standard deviations between walking with and without an AFO, using a paired t-test for sample size estimation purposes only, and a significance level of 0.025 to adjust for multiple testing. This sample size will also allow us to detect an effect size of 1.2 for differences between the two groups at each time point. Assuming a 10% drop-out rate, we will randomize 17 per group, for a total of 34 subjects. For statistical analysis, a linear mixed modeling approach (or generalized linear mixed model, as appropriate) will be used. This approach will allow us to detect differences within and between groups, and adjust for confounding variables. The main comparison of interest will be changes in walking distances due to wearing the AFO. The use of the crossover design will allow us to investigate several questions of interest: 1) If walking distances improve after wearing the AFO for 3-months; 2) If walking distances worsen over the first 3 months for subjects not wearing the AFO in the first period; and 3) If the improvement in walking distances from wearing the AFO for three months is retained over the second 3 months (no AFO). To evaluate the relationship between improvements in walking performance, physical activity, and quality of life, and improvements in morphometric parameters, muscle oxygenation, and muscle strength and endurance, multiple correlations will be used. The level of significance will be set at p=0.05.

Expected results/possible limitations: We hypothesize that an AFO intervention will increase walking performance, physical activity levels, and quality of life through improvements in the function of the muscles of the treated legs. If our hypothesis is correct, the AFO intervention is a new effective conservative intervention for patients with PAD. Because the premise is that the AFO will maintain overall torque and power while requiring a lower contribution from the leg muscles of patients, the patients will be able to walk further, placing less stress on their leg muscles, thereby allowing regeneration of structure and function of the muscles. Another possibility is that the patients experience an improvement in their walking performance, physical activity levels and quality of life but do not see improvements in muscular function of the legs. In this case, the

AFO would still be beneficial for patients to use. However, if none of the components of our hypothesis are correct, and neither the function and quality of life nor the muscle characteristics improve despite conscientious use of the AFO, then our study would direct us away from AFO-type treatments and towards other therapies and rehabilitation geared towards muscle health.

Specific Aim 3: Determine the feasibility of a three month AFO intervention

Approach: We will utilize Bowen and colleagues' standards for feasibility studies to measure the feasibility of using an AFO over three months in a random subset of 20 patients from Specific Aim 2. We will employ interviews and surveys throughout the three-month AFO intervention period to assess the following outcomes.

Outcomes

- 1) **Acceptability:** Interviews and a satisfaction survey will be implemented to assess satisfaction of using an AFO, intent to continue use, and perceived appropriateness measured. The research team will conduct interviews at 1.5 months, and three months. Interviews will last no longer than 30 minutes and will take place at the UNO Biomechanics Research Building. Satisfaction surveys for all participants will be completed during the final assessment in the Biomechanics Research Building.
- 2) **Demand:** Actual use and perceived demand will be measured using an accelerometer and interviews. An additional accelerometer will be given to the patient at the baseline visit. Battery life on these accelerometers can span over 30 days, especially with a lower sampling frequency of 1 Hz. Each month a new accelerometer will be mailed to participants and the package will include a pre-paid mailer for subjects to return the previous accelerometer for downloading data and charging. Additionally, patients will be contacted randomly three times during the 3-month study period to further assess the actual use. Perceived demand will be assessed via interview at baseline and at three months.
- 3) **Implementation:** Degree of use, success/failure of use, and factors affecting the ease/difficulty of use will be measured using interviews to determine implementation. Interviews will take no longer than 30 minutes and will occur at 1.5 months and 3-month time points.
- 4) **Practicality:** Measurements of the positive/negative effects of the AFO and ability of participants to effectively use the AFO will be made to determine the practicality of the intervention. We will assess these factors via interviews at three months.

Analysis for Specific Aim 3, Outcomes 1-4: Data from interviews will be transcribed and analyzed by the research team in NVivo 10 (QSR International Pty Ltd., Victoria, AU). Researchers will independently code transcripts and meet to reach agreement on major data themes. Emerging themes will be identified using a constant comparison approach. This approach allows for the development of explanations through patterns but also allows the coder to harness theory and prior knowledge or research to answer research questions.

Statistical analysis: Descriptive statistics will be used to summarize results of survey data. We will use counts and percents for categorical data, and means and standard deviations for quantitative data. Associations between walking distance variables and acceptability, use, and practicality variables will be examined using t-tests for dichotomous variables and correlations for continuous variables.

Expected results/possible limitations: We expect that an AFO intervention will be feasible to implement for three months in patients with PAD. If our hypothesis is correct, the study will establish the AFO as a new intervention that will likely be easily adopted by patients. It is also possible that the intervention does not prove feasible in one or more areas. If that happens, the study results will provide specific information on which aspects of the application of AFO treatment are not feasible. Those area(s) can then be further evaluated and potentially improved. Importantly, the results will inform the importance of these areas to feasibility of all interventions for the PAD patient group, not just the AFO intervention proposed in the current study.

Table 2: Project Timeline	1 st Year	2 nd Year	3 rd Year	4 th Year	5 th Year
Subject recruitment	XXXXXX	XXXXXX	XXXXXX	XXXXXX	XXX
Baseline assessment	XXXX	XXXXXX	XXXXXX	XXXXXX	
AFO and Control Intervention Arms	XXX	XXXXXX	XXXXXX	XXXXXX	XXX
Post AFO and Control assessments	XX	XXXXXX	XXXXXX	XXX	XXX
Data analysis		XXXXXX	XXXXXX	XXXXXX	XXXXXX
Abstract/manuscript development		XXX	XXXXXX	XXXXXX	XXXXXX
Grant writing				XXXXXX	XXXXXX

References

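### Both aims are sized at a reduced alpha for multiple testing, but the only analysis level stated is 0.05, with no statement of whether it is per test or overall and no rule for the two walking distances

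*Combined protocol and SAP*

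**What the plan says.** **Aim 1** (Combined protocol and SAP, section 4, Specific Aim 1, Statistical analysis). The sizing rests on both distances: "The sample size was calculated to detect effect sizes observed in pilot data for initial and absolute walking distances". It continues: "A sample size of 50 subjects will provide 84% power to detect differences of 0.47 standard deviations", by a paired t-test used for sizing only, at "a significance level of 0.02 to informally adjust for multiple testing". The analysis itself is a mixed model, and the paragraph closes: "The level of significance will be set at 0.05".

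**Aim 2** (section 4, Specific Aim 2, Statistical analysis). Thirty subjects give 80% power for 0.59 SD at "a significance level of 0.025 to adjust for multiple testing". The same N is said to "detect an effect size of 1.2 for differences between the two groups at each time point". The paragraph singles out change in walking distances with the AFO as its principal comparison, lists three questions the crossover can answer, describes the correlation analyses, and then sets the level at p=0.05.

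**Other outcomes.** The Aim 1 Approach paragraph states: "Walking performance will include measurement of initial and absolute walking distances, and lower extremity torque and power". Under Outcomes, item 2, it adds that "our primary lower extremity function outcome measures will be ankle and hip plantarflexor torque and power".

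Neither aim states a multiplicity procedure, a testing order, a rule for combining the two distances, or any other analysis level.

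**The concern.** A smaller alpha in a sample size calculation buys extra power. It controls false positives only if the tests are judged at that alpha, or by a procedure that has the same effect. Here the reduced level appears in the sizing sentences and 0.05 appears in the analysis sentences, with nothing to connect them.

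The plan therefore does not fix which p-value on a walking distance counts as a positive result. A p of 0.04 on initial distance, with absolute distance not significant, could be reported as success or as failure, and both reports would be consistent with the text. If it counts as success, the protection that the sizing provided for is lost.

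**Working it through.** **Inputs from the plan.** Aim 1: n=50, d=0.47 (43.4/93 = 0.467), alpha 0.02, stated power 84%. Aim 2: n=30, d=0.59, alpha 0.025, stated power 80%. Analysis level: 0.05 in both.

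**Assumptions.** Tests are two-sided; the plan does not state sidedness, but two-sided reproduces both power figures. The correlation r between the two test statistics is not given, so r = 0, 0.5 and 0.8 are shown. The paired t stands in for the mixed model, as in the plan's own sizing.

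**1. Reproducing the stated power.**
- Normal approximation: power = Φ(d√n − z(1−α/2)).
- Exact: noncentral t with n−1 degrees of freedom and noncentrality d√n.
- Aim 1: d√n = 0.47 × √50 = 3.323. At 0.02 the normal approximation is Φ(3.323 − 2.326) = 84.1%, which matches the stated 84%. The exact paired t at 0.02 (critical value 2.405) gives 81.7%.
- Aim 2: d√n = 0.59 × √30 = 3.232. The exact paired t at 0.025 (critical value 2.364) gives 80.2%, which matches the stated 80%. The normal approximation gives 83.9%.

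**2. Chance of at least one false positive when neither distance is affected and either may support the claim.** For r=0 this is 1 − (1−α)²: at 0.05, 1 − 0.95² = 9.75%; at 0.025, 1 − 0.975² = 4.94%. For other r it is 1 − P(|Z1|<c, |Z2|<c) under a bivariate normal, with c = 1.960 at 0.05 and 2.241 at 0.025.

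| r | 0.05 each | 0.025 each |
|---|---|---|
| 0 | 9.75% | 4.94% |
| 0.5 | 9.07% | 4.65% |
| 0.8 | 7.81% | 4.02% |

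The rate roughly doubles at every r.

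**3. If both distances must be significant at 0.05.** With no effect on either, the chance that both pass is 2 × 0.05 minus the first column: 0.25%, 0.93% and 2.19%. If one distance has a real effect and the other has none, it is at most 5%. There is no inflation.

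**4. Power if the adjustment is carried into the tests by Holm.** With two tests, Holm rejects a distance if its p is at most 0.025, or if its p is at most 0.05 and the other's is at most 0.025. No distance is ever held to a level below 0.025, so power at 0.025 is a floor whatever the other distance does.
- Aim 1 (n=50, d=0.47): 84.0% at 0.025; 90.3% at 0.05.
- Aim 2 (n=30, d=0.59): 80.2% at 0.025; 87.8% at 0.05.

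**5. Smallest significant mean gain,** t(1−α/2, n−1)/√n. Aim 1: 2.010/√50 = 0.284 SD at 0.05, and 2.312/√50 = 0.327 SD at 0.025. Aim 2: 2.045/√30 = 0.373 SD, and 2.364/√30 = 0.432 SD. With the pilot SD of 93 m for initial distance, the Aim 1 thresholds are 0.284 × 93 = 26.4 m and 0.327 × 93 = 30.4 m.

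**The case against.** The strongest reply is that 0.05 may be the overall level. In Aim 2, 0.025 is exactly 0.05/2, so 0.05 overall with 0.025 for each distance is coherent. The between-group figure of 1.2 SD with 15 per group also fits 0.025 (81.5% power). The documents allow this reading, but they do not state it. It is weaker in Aim 1, where 0.05/0.02 = 2.5 is not a whole number of tests. A reader might infer that the plan definitely tests each distance at 0.05 and has dropped its adjustment. The text does not establish that, and in Aim 2 the 0.05 sentence may concern only the correlations, which would leave the principal comparison with no stated level.

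It can also be said that the family is clear enough, since Aim 1 is sized on the two distances and Aim 2 makes them its principal comparison. That largely stands. What is missing is the success rule and the level. A reader might go further and build a six-test family by adding ankle and hip torque and power, because Outcomes item 2 calls them primary. That label is confined to the lower extremity function data and reads as the lead measures within that domain. Neither aim gives an effect size or power for them, so error rates for a six-test family are not a fair charge against this plan.

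Finally, Aim 1 calls its adjustment informal. That is candid, but the word is absent from Aim 2, and it does not tell the analyst which level to apply.

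**Conclusion.** The point holds in this form: the adjustment appears in the sizing of both aims and is not carried into any stated test, and the plan says neither whether 0.05 is per test or overall nor whether one or both distances must succeed.

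The size is conditional. With 0.05 per test and an either-distance claim, the family error is 7.8% to 9.8%, against 4.0% to 4.9% at 0.025 each, over r from 0.8 to 0. With both distances required, or with 0.05 as an overall level that is then applied, there is no inflation. The textual gap is certain; the inflation depends on a rule that the plan does not give.

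Two stronger inferences are not supported. The sample sizes are not undermined, because sizing at a smaller alpha is conservative. Nor do the documents show that 0.02 is a misprint for 0.025. The exact t at 0.025 happens to give 84.0%, but the normal approximation at the stated 0.02 gives 84.1%, so the printed figures are consistent as they stand. This merits only a query about the method. The point should be fixed before analysis, because it decides how the main results are read.

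**What to change.** In each aim, replace the 0.05 sentence with: *The AFO effects on initial and absolute walking distance are the confirmatory family, tested two-sided by Holm at family level 0.05. All other tests, including torque and power, are outside the family and reported at nominal 0.05.* In Aim 2, list the between-group comparisons at each time point, questions 2 and 3, and the correlations among the tests outside the family. Also name the one contrast per distance there, for example the within-subject AFO-period versus control-period effect from the mixed model; otherwise the family remains undefined.

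Two alternatives would also settle the matter, and the choice is the sponsor's:
- **One primary distance at 0.05.** Power is 90.3% in Aim 1 if it is initial distance (d=0.47), and 87.8% in Aim 2 (d=0.59). The other distance becomes supportive.
- **Both distances required at 0.05.** No inflation, but harder to meet. In Aim 2, with d=0.59 on both, power to succeed on both lies between 2 × 0.878 − 1 = 75.6% and 87.8%, depending on r.

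**Cost of the Holm wording.** There is no change to N, visits or data collection. A p-value between 0.025 and 0.05 on one distance is no longer confirmatory when the other does not reach 0.025. Power for a distance does not fall below 84.0% (Aim 1, d=0.47) or 80.2% (Aim 2, d=0.59). How far above that floor Aim 1 sits depends on the absolute-distance effect of 1.29 SD, which comes from four pilot patients, so the floor is the safer figure to quote.

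**Minor query.** State whether Aim 1's 84% is a normal approximation at 0.02; the exact paired t at that level gives 81.7%.
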